# Table 5–1: Schedule of study assessments

	-	ctive Base Period 8 weeks)	eline		Treatmen (12 we			Early discontinuation	Transition Period (2 weeks)/ Down Titration Period (4 weeks)	Study Drug-Free Period (2 weeks) a
Assessments	V1	V2	V3	V4	V5	V6	V7	EDV	V8	Safety Visit
	W -8	W -4	W 0	W 2	W 4	W 8	W 12		W 14/W 16	W 18
Laboratory safety assessments j	Х		Х	Х	Х	Х	X	Xď	Х	Х
Pregnancy test 	Х	Х	Х	X	X	X	Х	X d	Х	X
BRV plasma level m				Х	X	Х	X	X d	X n	
AE reporting	Х	Х	Х	Х	X	X	Х	Х	Х	X
C-SSRS	Х	Х	Х	X	X	X	Х	Х	Х	X
Medical procedures	Х	Х	Х	X	XO	XC	X	Х	Х	Х
Concomitant AED(s)/VNS settings	Х	X	X	X	S	X	X	Х	Х	X
Concomitant non-AED(s)	Х	X	X	X	X	X	Х	Х	Х	X
IMP dispensing			X	X	X	Х	Х	X d		
IMP return/accountability				X	X	Х	Х	X d	Х	
End of study status					)			Х	X k	X

AE=adverse event; AED=antiepileptic drug; BRV=brivaracetam; C-SSRS=Columbia-Suicide Severity Rating Scale; CT=computed tomography; DRC=daily record card; ECG=electrocardiogram; eCRF=electronic case report form; EDV=early discontinuation visit EEG=electroencephalogram; ID=identification card; IMP=investigational medicinal product; IVRS/IWRS=interactive voice response system/interactive web response system; MAP=managed access program; MRI=magnetic resonance imaging; LTFU=long term follow-up; W=week; V=Visit; VNS=vagal nerve stimulation

Note: Prior to entry into LTFU or MAP, the informed consent should be obtained from the subject at the end of Treatment Period (Visit 7) (Section 5.1.1).

a Safety Visit is not needed for subjects who discontinued before randomization.

b Subject is randomized at V3 once all inclusion/exclusion criteria are met.

c Vital signs (supine or sitting pulse rate and blood pressure after 5 minutes rest).

d Assessment to be conducted in subjects who discontinued after randomization.

e Height will be recorded at V1 only.

f Baseline ECG has to be scheduled and results received before V3. An ECG at the Safety Visit will be performed only if abnormal at V7/EDV.

g Baseline EEG has to be scheduled and results received before V3 if no appropriate EEG available within the last 5 years.

h A CT scan or MRI has to be scheduled and results received before V3 if no previous CT scan or MRI available within the last 2 years.

i Seizure counts are collected on the subject's DRC on a daily basis.

Confidential

UCB
Clinical Study Protocol

des and times for the send of j Laboratory assessment: safety assessment includes hematology, blood chemistry, and urinalysis. Eligibility of subjects will be based on laboratory samples collected at V1. The result of the creatinine clearance will be provided by the central laboratory for all visits and the results at V1 will be used to determine eligibility of the subject. k Only Transition Period

Serum pregnancy at V1 only. Urine pregnancy test will be used at other visits.

m Concentrations of BRV will be determined in plasma samples. Date and time of sampling will be recorded. Dosing dates and times for the actual 3 previous BRV doses will be recorded in the eCRF.

n At V8, concentrations of BRV will be evaluated only in the Transition Period.

° If subjects will not enter to LTFU or MAP, a DRC is dispensed.

\* Subjects with an EDV at any time during the Treatment Period should proceed through the 4-week Down-Titration Period and 2-week Study Drug-Free Period

### 5.4 Rationale for study design and selection of dose

Consistent with the previous fixed dose Phase 3 studies N01253, N01252 and N01358 in EU/US, EP0083 will include an 8-week Baseline Period and a 12-week Treatment Period. The primary stil2tion efficacy variable is the partial seizure frequency per 28 days during the 12-week Treatment Period.

Brivaracetam 50 to 200mg/day is approved as the effective dose for adults in EU/US. The treatment arms of EP0083 have been decided from the minimum/maximum dose approved.

### 6 SELECTION AND WITHDRAWAL OF SUBJECTS

After the number of prior LEV use subjects are randomized to 30% of the total study population, only LEV naive subjects will be entered in EP0083.

- To be eligible to participate in this study, all of the following criteria must be met: 1. An Institutional Review Board (IRB)/Independent Ethics of written Informed Compared legal representative. The Informed Consent form or a specific Assent form, where required, will be signed and dated by minors.
  - 2. Subject/legal representative is considered reliable and capable of adhering to the protocol (eg, able to understand and complete diaries), visit schedule, or medication intake according to the judgment of the Investigator.
  - 3. Subjects (male or female) from 16 to 80 years of age at Visit 1, both inclusive. Subjects who are not legal adults may only be included where legally permitted and ethically accepted.
  - 4. Subjects with a body weight  $\geq$ 40kg during Baseline Period.
  - 5. Female subjects without childbearing potential (postmenopausal for at least 2 years, bilateral oophorectomy or tubal ligation, complete hysterectomy) are eligible. Female subjects with childbearing potential are eligible if they use a medically accepted contraceptive method. Oral or depot contraceptive treatment with at least approved dosage of ethinylestradiol per intake in each country where this study is conducted (if subjects is taking any enzyme inducer such as carbamazepine, phenobarbital, primidone, phenytoin, oxcarbazepine, St. John's Wort or rifampicin, the dosage of ethinylestradiol should have been modified according to the guidelines for contraceptive treatment in each country), monogamous relationship with vasectomized partner, or barrier contraception are acceptable methods. The subject must understand the consequences and potential risks of inadequately protected sexual activity, be educated about and understand the proper use of contraceptive methods, and undertake to inform the Investigator of any potential change in status. Abstinence will be considered as an acceptable method of contraception if the Investigator can document that the subject agrees to be compliant.
  - 6. Well-characterized focal epilepsy/epileptic syndrome according to the 1989 ILAE classification.

, Stilor

- 7. Presence of an electroencephalogram (EEG) reading compatible with the clinical diagnosis of focal epilepsy within the last 5 years. Baseline EEG has to be scheduled and results received before Visit 3 if no appropriate EEG available within the last 5 years.
- 8. Presence of a brain magnetic resonance imaging (MRI)/computed tomography (CT) scan performed within the last 2 years. A CT scan or MRI has to be scheduled and results received before Visit 3 if no previous CT scan or MRI available within the last 2 years.
- 9. Subjects having at least 8 partial seizures (according to the 1981 ILAE classification) during the 8-Week Baseline Period with at least 2 partial seizures during each 4-week interval of the Baseline Period.
- 10. Subjects having at least 2 partial seizures whether or not secondary generalization per month during the 3 months preceding Visit 1.
- 11. Subjects uncontrolled while treated by 1 or 2 permitted concomitant AED(s). Vagal Nerve Stimulation (VNS) is allowed and will be counted as a concomitant AED.
- 12. Permitted concomitant AED(s) and VNS being stable and at optimal dosage for the subject from at least 4 weeks (12 weeks for phenobarbital, phenytoin, and primidone) before Visit 1 and expected to be kept stable during whole study period.

# 6.2 Exclusion criteria

Subjects are not permitted to enroll in the study if any of the following criteria is met:

- 1. Subject previously randomized within this study or any other prior study with BRV as a dosing arm.
- 2. Simple partial seizure (1981 ILAE classification) nonmotor as only seizure type.
- 3. Subject has experienced febrile seizures exclusively. The occurrence of febrile seizures in addition to other unprovoked seizures is not exclusionary.
- 4. Subject has participated in another study of an investigational medication (or a medical device) within the last 30 days or is currently participating in another study of an investigational medication (or a medical device).
- 5. Subject is currently treated with LEV.
- 6. Subject has taken LEV within 90 days prior to Visit 1.
- 7. Subject has any medical or psychiatric condition that, in the opinion of the Investigator, could jeopardize or would compromise the subject's ability to participate in this study.
- 8. Subject has a known hypersensitivity to any components of the IMP, or any of its excipients.
- 9. Subject/legal representative not able to read and understand the Informed Consent form, Assent form, or daily record card (DRC) instructions.
- 10. Subject has severe cognitive impairment or mental retardation as per Investigator assessment
- 11. Subject whose seizures could not be reliably counted on a regular basis due to their fast and repetitive occurrence (clusters or flurries).

ation

- 12. Subject has history or presence of status epilepticus during the year preceding Visit 1 or during Baseline.
- 13. Subject has history or presence of known psychogenic nonepileptic seizures.
- 14. Subject has taken vigabatrin for 24 weeks prior to Visit 1. Subject with history of vigabatrin use but either no visual fields examination report available including standard static (Humphrey or Octopus) or kinetic perimetry (Goldman) or results of these examinations are abnormal, even though vigabatrin was stopped before 24 weeks.
- 15. Subject taking any drug with possible central nervous system (CNS) effects except if stable from at least 4 weeks before Visit 1 and expected to be kept stable during whole study period.
- 16. Subject taking any drug that significantly influences the metabolism of BRV (cytochrome P450 strong inducers such as rifampin/rifampicin) except if the dose has been kept stable at least 4 weeks before Visit 1, and is expected to be kept stable during the Treatment Period.
- 17. Subject has history of cerebrovascular accident, including transient ischemic attack, in the last 24 weeks.
- 18. Subject has severe cardiovascular disease or peripheral vascular disease.
- 19. Subject has presence of any sign (clinical or imaging techniques) suggesting rapidly progressing (ie, not expected to stay stable during study participation) brain disorder or brain tumor. Stable arteriovenous malformations, meningiomas, or other benign tumors may be acceptable.
- 20a. Subject has any clinical conditions (eg, bone marrow suppression, severe renal impairment with creatinine clearance [CLcr] <30 ml/min/1.73 m^2) which impair reliable participation in the study or necessitate the use of medication not allowed by protocol.
- 21. Subject has chronic hepatic disease.
- 22. Subject has presence of a terminal illness.
- 23. Subject has presence of a serious infection.
- 24. Subject has history of severe adverse hematologic reaction to any drug.
- 25. Subject has severe disturbance of hemostasis.
- 26. Subject has >2xULN of any of the following: alanine aminotransferase (ALT), aspartate aminotransferase (AST), alkaline phosphatase (ALP), or >ULN total bilirubin (≥1.5xULN total bilirubin if known Gilbert's syndrome).

If subject has elevations only in total bilirubin that are >ULN and <1.5xULN, fractionate bilirubin to identify possible undiagnosed Gilbert's syndrome (ie, direct bilirubin <35%)

For randomized subjects with a Baseline result >ULN for ALT, AST, ALP, or total bilirubin, a Baseline diagnosis and/or the cause of any clinically meaningful elevation must be understood and recorded in the electronic Case Report form (eCRF).

If subject has >ULN ALT, AST, or ALP that does not meet the exclusion limit at screening, repeat the tests, if possible, prior to dosing to ensure there is no further ongoing clinically

relevant increase. In case of a clinically relevant increase, inclusion of the subject must be discussed with the Medical Monitor.

- 27a. Subject has clinically significant laboratory abnormality that may increase the risk 1.21101 associated with study participation or may interfere with the interpretation of study results, according to the judgment of the Investigator.
- 28. Subject has clinically significant ECG abnormalities according to the Investigator.
- 29. Subject has a lifetime history of suicide attempt (including an active attempt, interrupted) attempt, or aborted attempt), or has suicidal ideation in the past 6 months as indicated by a positive response ("Yes") to either Question 4 or Question 5 of the Columbia-Suicide tin thereof Severity Rating Scale (C-SSRS) at Visit 1.
- 30. Subject has known multiple drug allergies or severe drug allergy.
- 31. Subject is pregnant or lactating.
- 32. Subject has known alcohol or drug addiction or abuse within the last 2 years.
- 33. Investigators, co-Investigators, their spouses or children, or any study collaborators. If the Investigator has any other doubts concerning the eligibility, he/she should consult UCB Study Physician or representative for clarification.

### Withdrawal criteria 6.3

Subjects are free to withdraw from the study at any time, without prejudice to their continued care.

Subjects should be withdrawn from the study if any of the following events occur:

- Withdrawal for safety reasons by the Investigator such as a worsening of the seizure profile, eg, occurrence of status epilepticus, seizure clustering, or generalized tonic-clonic seizure, if unknown for the subject
- Subject develops an illness that would interfere with his/her continued participation.
- Subject is noncompliant with the study procedures or medications in the opinion of the Investigator.
- Subject takes prohibited concomitant medications as defined in this protocol.
- Subject or legal guardian withdraws his/her consent.
- There is confirmation of a pregnancy during the study, as evidenced by a positive pregnancy test.

The sponsor or a regulatory agency requests withdrawal of the subject.

Subject has active suicidal ideation without specific plan as indicated by a positive response ("Yes") to Ouestion 4 of the "Since Last Visit" version of the C-SSRS. The subject should be referred immediately to a Mental Healthcare Professional and may be withdrawn from the study based upon the Investigator's judgment of benefit/risk of continuing the subject in the study/on study medication.

• Subject has active suicidal ideation with a specific plan as indicated by a positive response ("Yes") to Question 5 of the "Since Last Visit" version of the C-SSRS. The subject should be referred immediately to a Mental Healthcare Professional and must be withdrawn from the study.

Investigators should attempt to obtain information on subjects in the case of withdrawal. For subjects considered as lost to follow-up, the Investigator should make an effort (at least 1 phone call and 1 written message to the subject), and document his/her effort (date and summary of the phone call and copy of the written message in the source documents), to complete the final evaluation. All results of these evaluations and observations, together with a narrative description of the reason(s) for removing the subject, must be recorded in the source documents. The eCRF must document the primary reason for withdrawal.

Investigators should contact the Medical Monitor, whenever possible, to discuss the withdrawal of a subject in advance.

# 6.3.1 Potential drug-induced liver injury IMP discontinuation criteria

Subjects with potential drug-induced liver injury (PDILI) must be assessed to determine if IMP must be discontinued. In addition, all concomitant medications and herbal supplements that are not medically necessary should also be discontinued.

The PDILI criteria below require immediate and permanent discontinuation of IMP:

- Subjects with either of the following:
  - ALT or AST  $\geq$ 5xULN
  - ALT or AST  $\geq$ 3xULN and coexisting total bilirubin  $\geq$ 2xULN

The PDILI criterion below requires immediate discontinuation of IMP:

• Subjects with ALT or AST ≥3xULN who exhibit temporally associated symptoms of hepatitis or hypersensitivity. Hepatitis symptoms include fatigue, nausea, vomiting, right upper quadrant pain or tenderness. Hypersensitivity symptoms include fever (without clear alternative cause), rash, or eosinophilia (ie, >5%).

The PDILI criterion below allows for subjects to continue on IMP at the discretion of the Investigator.

• Subjects with ALT or AST ≥3xULN (and ≥2x Baseline) and <5xULN, total bilirubin <2xULN, and no eosinophilia (ie, ≤5%), with no fever, rash, or symptoms of hepatitis (eg, fatigue, nausea, vomiting, right upper quadrant pain or tenderness).

Evaluation of PDILI must be initiated as described in Section 11.2.1. If subjects are unable to comply with the applicable monitoring schedule, IMP must be discontinued immediately.

Investigators should attempt to obtain information on subjects in the case of IMP discontinuation to complete the final evaluation. Subjects with PDILI should not be withdrawn from the study until investigation and monitoring are complete. All results of these evaluations and observations, as well as the reason(s) for IMP discontinuation and subject withdrawal (if applicable), must be recorded in the source documents. The eCRF must document the primary reason for IMP discontinuation.

### 7 STUDY TREATMENT(S)

### Description of investigational medicinal product(s) 7.1

Oral film-coated tablets of BRV 25mg, BRV 50mg, and matching PBO tablets will be used in

After an 8-Week Baseline Period and once the subject has fulfilled the eligibility criteria, he/she will be randomized to 50mg/day group, 200mg/day group or PBO group, and enter the double-blind Treatment Period (Visit 3 to Visit 7).

During the Treatment Period, subjects will be treated with BRV 50mg/day, BRV 200mg/day, or the matching PBO tablets in a double-blinded manner. Study medication should be given as 2 equally divided doses administered twice daily except the last week of down-titration. Study medication in the last week of down-titration is given only in the morning. The first intake of newly dispensed study medication should occur in the evening of each visit. Subjects should take IMP according to instructions provided by Investigator.

At the end of the Treatment Period (Visit 7), the subjects entering into the LTFU study or MAP will enter the Transition Period or the subjects not entering into the LTFU study or MAP will enter the Down-Titration Period followed by a Study Drug-Free Period.

The Transition Period (2 weeks) will consist of the following:

- For subjects randomized to BRV 50mg/day group or PBO group, keep same dose as Treatment Period during the Transition Period.
- For subjects randomized to BRV 200mg/day group, the Transition Period will consist of the • following: 2 weeks at BRV 150mg/day.

The Down-Titration Period (4 weeks) will consist of the following:

- For subjects randomized to PBO group, keep PBO during the Down-Titration Period.
- For subjects randomized to BRV 50mg/day group, the Down-Titration Period will consist of the following: 1 week at BRV 25mg/day followed by 3 weeks at PBO.
- For subjects randomized to BRV 200mg/day group, the Down-Titration Period will consist of the following: I week at BRV 150mg/day, 1 week at BRV 100mg/day, 1 week at BRV 50mg/day, followed by 1 week at BRV 25mg/day.

The down-titration procedure needs to be applied in case of early discontinuation or completion without conversion to the LTFU study or MAP.

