# Table 11–2: Required investigations and follow-up for PDILI

Laboratory	value		Immediate		Follow up	
ALT or AST	Total bilirubin	Symptoms a of hepatitis or hypersensitivity	Consultation requirements	Actions	Testing	Evaluation
≥3xULN	≥2xULN b	NA	Hepatology consult. c Medical Monitor must be notified within 24 hours (eg, by laboratory alert) and subject discussed with	Immediate, permanent IMP discontinuation.	Essential: Must have repeat liver chemistry values and additional testing completed ASAP (see	Monitoring of liver chemistry values at least twice per week until values normalize, stabilize, or return to within baseline values. d
≥3xULN	NA	Yes	Medical Monitor ASAP.	Immediate, temporary or permanent, IMP discontinuation.	Section 11.2.1.3); recommended to occur at the site with HCP.	
≥5xULN (and ≥2x Baseline)	<2xULN	No	Discussion with Medical Monitor required. Hepatology consult required if ALT/AST ≥8xULN	Immediate IMP discontinuation	Essential: Every attempt must be made to have repeat liver chemistry values and additional testing completed within 48 hours at the site with HCP (see Section 11.2.1.3).	

- rut Confidential

Laboratory value			Immediate		Follow up	
ALT or AST	Total bilirubin	Symptoms a of hepatitis or hypersensitivity	Consultation requirements	Actions	Testing	Evaluation

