≥3xULN (and ≥2x Baseline) and <5xULN	<2xULN	No	Discussion with Medical Monitor required if the criterion that allows for IMP continuation is met.	
 
Further investigation – immediate IMP discontinuation not required (see Section 11.2.1.2).
 
IMP discontinuation required if any of the following occur:
 
Subject cannot comply with monitoring schedule.
 
Liver chemistry values continue to increase.
 
Liver chemistry values remain ≥3xULN (and ≥2xBaseline) after 2 week monitoring without stabilization or evidence of resolution.
 
	Not required unless otherwise medically indicated (at discretion of Investigator	
 
Monitoring of liver chemistry values a least twice per week for 2 weeksd
 
Immediate IMP discontinuation required if:
 
liver chemistry values continue to increase.
 
After 2 weeks of monitoring liver chemistry values:
 
Liver chemistry values remain ≥3xULN (and ≥2x Baseline) afte 2 weeks of monitoring without stabilization or evidence of resolution
 
Continue to monitor until values normalize, stabilize, or return to withit Baseline valuesd
 

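### The early-discontinuation taper and dispensing rules carry no exception for subjects whose study drug was stopped permanently for liver injury (Protocol 7.2 and Table 5-1 against 6.3.1)

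*Protocol*

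**What the plan says.** **The liver stop.** Protocol 6.3.1 names two criteria that "require immediate and permanent discontinuation of IMP": ALT or AST at or above 5xULN, and ALT or AST at or above 3xULN with total bilirubin at or above 2xULN. It adds: "Subjects with PDILI should not be withdrawn from the study until investigation and monitoring are complete".

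**The taper.** Protocol 7.2 (Treatment(s) to be administered) sets out a 4-week Down-Titration Period for each arm and ends with the general rule: "The down-titration procedure needs to be applied in case of early discontinuation". The same sentence covers subjects who complete without converting to the follow-up study or access program.

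**The EDV.** A starred note printed before Section 5.4 sends subjects with an EDV during the Treatment Period through down-titration and then the drug-free period. In Table 5-1 the IMP dispensing row is marked at the EDV, and the only condition, footnote d, is that the subject discontinued after randomization.

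**The liver follow-up table.** Table 11-2 gives the action for each of four patterns. The bilirubin row reads "Immediate, permanent IMP discontinuation", the symptomatic row "Immediate, temporary or permanent, IMP discontinuation", and the ≥5xULN row "Immediate IMP discontinuation". For ≥3x to <5xULN without symptoms it reads "IMP discontinuation required if any of the following occur". Neither Table 11-2 nor Sections 11.2.1 to 11.2.1.4 mention down-titration.

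**The concern.** A permanent stop for suspected liver injury and a compulsory taper cannot both be followed in the same subject. Staff who run an EDV from 7.2 and the visit schedule find an instruction to dispense and taper, with nothing that points them to 6.3.1. What is at stake is re-exposure to the suspect drug in a subject with raised transaminases.

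There is also a reporting consequence. A subject who correctly stops without a taper fits none of the post-treatment periods that the SAP defines, although the SAP reports adverse events by period.

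**Working it through.** The plan states no figure on this point. The check compares the texts and then bounds the dose.

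**1. Does any taper or dispensing instruction exempt the liver stop?**

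- Protocol 7.2: applies to early discontinuation generally; no liver exception.
- Starred note: applies to an EDV during the Treatment Period; no liver exception. It is worded as should and may belong to the Section 5.3 schematic, which is not shown.
- Table 5-1, EDV dispensing: limited only by footnote d; no liver exception.

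For comparison, Protocol 11.1.4 (Pregnancy) gives an immediate stop as an alternative to down-titration. The liver sections have no matching sentence.

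**2. When would the conflict arise?** At the EDV, but the documents do not fix when that is. Protocol 8.8 ties the visit to leaving the study, and 6.3.1 keeps liver cases in the study during work-up, which suggests a later EDV. SAP 3.2.2 ties the EDV to stopping treatment early, which suggests an earlier one. The conflict exists under either reading.

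**3. Which liver stops are affected?**

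| Pattern | Protocol 6.3.1 | Table 11-2 |
|---|---|---|
| ≥3xULN with bilirubin ≥2xULN | permanent | permanent |
| ≥5xULN | permanent | immediate; permanence not stated |
| ≥3xULN with symptoms | immediate; permanence not stated | temporary or permanent |
| ≥3x to <5xULN, no symptoms | may continue at the Investigator's discretion | stop if a listed condition occurs; permanence not stated |

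The conflict is certain for the first two patterns. For the other two it arises only if the stop is permanent or still in force at the EDV. The same holds for the further trigger in 6.3.1: "If subjects are unable to comply with the applicable monitoring schedule, IMP must be discontinued immediately".

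**4. Upper bound on the dose.** Inputs are the weekly steps in Protocol 7.2, at a nominal 7 days each. Formula: sum of (7 days × daily dose).

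- 200 mg/day arm: 7 × (150 + 100 + 50 + 25) = 7 × 325 = 2275 mg over 28 days.
- 50 mg/day arm: 7 × 25 = 175 mg over 7 days, then placebo for 3 weeks.
- Placebo arm: 0 mg.

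Under 6.3.1 the intended dose after a permanent stop is 0 mg in every arm.

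**5. Where do later events of an untapered subject go?** In SAP 3.2.2 the Treatment Period ends at Visit 7 or the EDV. The Down-Titration Period requires some IMP to be taken in it, and the Study Drug-Free Period requires entry into Down-Titration. The Transition Period requires IMP and planned entry into follow-up treatment. Events after the EDV therefore have no defined period. SAP 10.2 classifies events by these periods. SAP 10.2.1 tabulates by period and describes its combined tables as the sum of the named periods. SAP 5.1.1 nevertheless expects subjects who discontinue without entering Down-Titration.

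**The case against.** The strongest reply is that 6.3.1 already settles the matter. It is the specific safety rule, and a permanent stop needs no further words to exclude more drug. Section 11.2.1.2 refers the Investigator back to it. Section 11.2.1.1 requires notice to the Medical Monitor within 24 hours and a discussion of the case. Section 12.1 allows departures from protocol to avert immediate hazard. Section 7.2 also has subjects take IMP as the Investigator instructs, and a subject already off drug has no dose to step down. Exceptions may simply be placed in event-specific sections: 7.2 does not mention the pregnancy alternative either. Finally, part of the 7.2 text, the rest of the 8.8 list and the Section 5.3 schematic cannot be read, so a qualifier there cannot be ruled out.

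All of this lowers the probability, and most sites would not give the taper. None of it puts an exception into the readable text of 7.2, the starred note or Table 5-1. The pregnancy section in fact shows the protocol naming an immediate stop as an alternative to the taper where one is intended. A stop rule should not depend on staff working out which of two instructions prevails.

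Three stronger readings are tempting:

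- A reader might infer that the plan would put liver-injured subjects back on drug. The documents show only conflicting text, with safeguards around it.
- A reader might infer that the EDV necessarily follows the stop by some interval. Protocol 8.8 and SAP 3.2.2 point different ways on this.
- A reader might infer that Table 11-2 contradicts 6.3.1 at ≥5xULN. The row is silent on permanence; it does not permit a restart.

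**Conclusion.** The point stands as a low-probability patient-safety inconsistency that should be corrected. For the two permanent-stop criteria, the general taper and dispensing instructions conflict with 6.3.1 when read as written, whenever the EDV occurs.

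The bounds of 2275, 175 and 0 mg assume that a site gives the complete taper in error. They are not expected doses. The documents give no frequency of these liver events, overall or by arm, so neither an average dose per subject nor a number of subjects affected can be supported. The SAP gap is separate and does not depend on any dosing error: it applies to every subject who stops without a taper.

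**What to change.** 1. **Protocol 7.2.** State that down-titration does not apply, and no IMP is dispensed, once IMP has been permanently discontinued under 6.3.1 or while it is on hold under those criteria. State also that the remaining EDV assessments, a Safety Visit 2 weeks after the last dose (the interval used in 11.1.4) and the Table 11-2 monitoring still take place. Cross-refer to this at the starred note and at the Table 5-1 EDV dispensing entry. Because the exception sits in 7.2, it also covers a liver case who stays to Visit 7 and completes without conversion.
2. **Table 11-2, ≥5xULN row.** Use the wording of the bilirubin row, "Immediate, permanent IMP discontinuation", to match 6.3.1.
3. **SAP 3.2.2.** Assign a study period, for example Study Drug-Free, to data after the last Treatment Period visit in subjects who do not enter Down-Titration, so that their treatment-emergent events are counted in the by-period and combined tables.

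I would not add a general permission to change concomitant AEDs from the date of the stop. Section 11.2.1.2 already lets the Investigator consider reducing or replacing concomitant drugs. A wider permission would allow AED changes inside the window of the primary variable, which is a trade-off that this correction does not need.

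The cost is a short protocol clarification and one SAP sentence. Sample size, power and alpha do not change. Abrupt withdrawal is a real downside, but 6.3.1 already requires it.
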